5. TREATMENT PLAN

5.1 Treatment Regimen

Following registration, participants will be randomized in a 2:1 ratio to either Arm A: a combination of Radium-223 and pembrolizumab or Arm B: Radium-223 alone.

Patients will be stratified based on:

- Baseline alkaline phosphatase <220 or ≥ 220
- Volume of bone metastases (high: ≥ 4 bone metastases including one beyond the axial skeleton vs. low: <4 bone metastases)
 Based on CHAARTED (ECOG 3805) criteria²⁴

Given the varied dosing of the two agents, we will refer to weeks on study instead of cycles.

Radium-223 55kBq/kg (1.49 μ Ci)/kg will be administered intravenously (IV) slowly over 1 minute every 4 weeks for a maximum of 6 doses. Weight used for dosing should be based on institutional standards. Radium-223 will be administered in the nuclear medicine suite at DFCI and at the corresponding department for participating investigational sites.

Pembrolizumab will be given only to patients randomized to the investigational arm (Arm A). Pembrolizumab will be given at a dose of 200mg intravenously every 3 weeks. It will be administered in the Yawkey Infusion Center at DFCI and at the corresponding department for participating investigational sites.

Treatment with both agents will be administered on an outpatient basis. Reported adverse events and potential risks are described in Section 7. No investigational or commercial agents or therapies other than those described below may be administered with the intent to treat the participant's prostate cancer.

No dose modifications will be made for either agent. If study agents are held for more than 12 weeks (for pembrolizumab) or 8 weeks (for Radium-223) due to study drug-related toxicity, the patient should be discontinued from the offending agent. Patients may continue on either agent alone if tolerating.

Agent	Premedication	Dose	Route	Schedule
Pembrolizumab	None unless	200mg	IV 30 minutes	Every 3 weeks (21 +/-3
	prior reaction;	(diluted	-5 min/+ 10	days)
	(see Table 6)	per	min	
		institution		*Should be given prior
		al		to radium on days
		guidelines		when they are given
		/package		together.
		insert)		
Radium-223	None	55kBq/kg	IV over 1	Every 4 weeks (28 +/-
		(1.49µCi)/	minute or	7 days) for 3 doses
		kg	longer per	followed by a break
			institutional	until radiologic disease
			standards	progression. Then the
				last 3 doses will be
				given every 4 weeks
				(28 +/-7 days)

Table 3: ARM A - Combination Investigational Arm

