6.1 Dose Delay Guidelines for Pembrolizumab

Adverse events (both non-serious and serious) associated with pembrolizumab exposure may represent an immunologic etiology. These adverse events may occur shortly after the first dose or several months after the last dose of treatment. Pembrolizumab must be withheld for drug-related toxicities and severe or life-threatening AEs as per the Table below.

If an irAE is suspected, a thorough evaluation should be conducted in an effort to possibly rule out neoplastic, infectious, metabolic, toxin or other etiologic causes prior to diagnosing an irAE. Serological, immunological, and histological (biopsy) data should be considered to support the diagnosis of an immune-related toxicity.

Table 5: Summary of Dosing Guidelines for Drug-Related Adverse Events (see more detailed recommendations for each event below the table)

Toxicity	Hold Treatment For Grade	Timing for Restarting Treatment	Discontinue Subject
Diarrhea/Colitis	2-3	Toxicity resolves to Grade 0-1.	Toxicity does not resolve within 12 weeks of last dose or inability to reduce corticosteroid to 10 mg or less of prednisone or equivalen per day within 12 weeks.
	4	Permanently discontinue	Permanently discontinue
AST, ALT, or	2	Toxicity resolves to Grade 0-1	Toxicity does not resolve within 12 weeks of last dose.
Increased Bilirubin	3-4	Permanently discontinue	Permanently discontinue
Type 1 diabetes mellitus (if new onset) or Hyperglycemia	T1DM or 3-4	Hold pembrolizumab for new onset Type 1 diabetes mellitus or Grade 3-4 hyperglycemia	Resume pembrolizumab when patients are clinically and metabolically stable.
	2	Toxicity resolves to Grade 0-1	Toxicity does not resolve within 12 weeks of last dose or inability to reduce corticosteroid to 10 mg or less of prednisone or equivalen per day within 12 weeks.
Hypophysitis	3	Hold until toxicity resolves to Grade 0-1 or permanently discontinue per treating investigator's discretion	Hold until toxicity resolves to Grade 0-1 or permanently discontinue per treating investigator's discretion
	4 or Recurrent Grade 2 or 3	Permanently discontinue	Permanently discontinue
Hyperthyroidism	3	Toxicity resolves to Grade 0-1	Toxicity does not resolve within 12 weeks of last dose or inability to reduce corticosteroid to 10 mg or less of prednisone or equivalen per day within 12 weeks.
	4	Permanently discontinue	Permanently discontinue

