Hypothyroidism	2-4	Therapy with pembrolizumab can be continued while treatment for the thyroid disorder is instituted	Therapy with pembrolizumab can be continued while treatment for the thyroid disorder is instituted.
Infusion Reaction	3-4	Permanently discontinue	Permanently discontinue
Myocarditis	1-2	Hold until toxicity resolves to Grade 0	Per physician discretion, treat with corticosteroids. If pembrolizumab held and corticosteroid required, manage as per Grade 3.
	3-4	Permanently discontinue	Permanently discontinue
Pneumonitis	2	Toxicity resolves to Grade 0-1	Toxicity does not resolve within 12 weeks of last dose or inability to reduce corticosteroid to 10 mg or less of prednisone or equivalen per day within 12 weeks.
rneunionius	3-4 or Recurrent Grade 2	Permanently discontinue	Permanently discontinue
Renal Failure or Nephritis	2	Toxicity resolves to Grade 0-1	Toxicity does not resolve within 12 weeks of last dose or inability to reduce corticosteroid to 10 mg or less of prednisone or equivalen per day within 12 weeks.
	3-4	Permanently discontinue	Permanently discontinue
All Other Drug-	Intolerable/ Recurrent Grade 2	Toxicity resolves to Grade 0-1	Toxicity does not resolve within 12 weeks of last dose or inability to reduce corticosteroid to 10 mg or less of prednisone or equivalen
Related Toxicity ¹	3 or Severe	Toxicity resolves to Grade 0-1	per day within 12 weeks.
	4	Permanently discontinue	Permanently discontinue

¹Patients with intolerable or persistent Grade 2 drug-related AE may hold study medication at physician discretion. Permanently discontinue study drug for persistent Grade 2 adverse reactions for which treatment with study drug has been held and that do not recover to Grade 0-1 within 12 weeks of the last dose.

Dosing interruptions are permitted in the case of medical / surgical events or logistical reasons not related to study therapy (e.g., elective surgery, unrelated medical events, patient vacation, and/or holidays). Subjects should be placed back on pembrolizumab within 12 weeks of the last dose, unless otherwise discussed with the Overall PI and Merck contact. The reason for interruption should be documented in the patient's study record.

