Collect past medical history relevant to the event. Any preexisting conditions not previously reported (e.g., drug allergy) should be entered into the Medical History eCRF.

C. Presentation of the Event:

Collect information on clinical presentation and potential contributing factors. This information should be summarized and entered in narrative format in the AE eCRF. Please use the available free-text fields, such as Signs and Symptoms. Note pertinent negatives where applicable to reflect that the information was collected. Any treatments administered should be entered on the Concomitant Medication eCRF.

D. Vitals Signs and Standard Laboratory Tests:

Measure vital signs (pulse, sitting BP, oral temperature, and respiratory rate) and record on the Vital Signs eCRF. Perform standard laboratory tests (CBC with manual differential and serum chemistry panel, including LFTs).

E. Focused Skin Examination:

Perform a focused skin examination. Information should be summarized and entered on the Adverse Experience eCRF as part of the narrative.

F. Dermatology Consult

Refer the subject to a dermatologist as soon as possible.

- For a "severe rash", the subject must be seen within 1-2 days of reporting the event.

- For clinically significant rash, the subject should be seen within 3-5 days.

The dermatologist should submit a biopsy sample to a certified dermatopathology laboratory or to a pathologist experienced in reviewing skin specimens. The site should provide the dermatologist with all relevant case history, including copies of clinical photographs and laboratory test results.

Other/Miscellaneous Immune Related Toxicities

The following AEs, regardless of grade, should be reported to the Sponsor-Investigator within 24 hours of the event:

- Myocarditis
- Pericarditis
- Pancreatitis

– Any additional Grade 3 or higher event, which the physician considers to be immune related

All attempts should be made to rule out other causes. Therapeutic specialists should be consulted as appropriate. However, the AE should be reported to the Sponsor-Investigator regardless of etiology.

Course of Action

Grade 2 events or Grade 1 events that do not improve with symptomatic treatment:

- Withhold pembrolizumab.
- Systemic corticosteroids may be indicated.
- Consider biopsy for confirmation of diagnosis.
- If pembrolizumab held and corticosteroid required, manage as per grade 3 below.

Grade 3 events:

Hold pembrolizumab

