- Treat with systemic corticosteroids at a dose of 1 to 2 mg/kg prednisone or equivalent once per day.

- When symptoms improve to Grade 1 or less, steroid taper should be started and continued over no less than 4 weeks.

- Permanently discontinue if any grade 3 or higher cardiac toxicity including myocarditis and pericarditis even if improves/resolves

- Permanently discontinue for inability to reduce corticosteroid dose to 10 mg or less of prednisone or equivalent per day within 12 weeks. Otherwise, pembrolizumab treatment may be restarted as specified in the protocol

Grade 4 events:

- Treat with systemic corticosteroids at a dose of 1 to 2 mg/kg prednisone or equivalent once per day.

– Discontinue pembrolizumab

Infusion Reactions

The following AE terms, regardless of grade, should be reported to the Sponsor-Investigator within 24 hours of the event:

- Allergic reaction
- Anaphylaxis
- Cytokine release syndrome
- Serum sickness
- Infusion reactions
- Infusion-like reactions

Please note, the AE should be reported to the Sponsor-Investigator regardless of etiology.

Course of Action

Refer to infusion reaction table below.

• **Management of Infusion Reactions**: Signs and symptoms usually develop during or shortly after drug infusion and generally resolve completely within 24 hours of completion of infusion. Table below shows treatment guidelines for subjects who experience an infusion reaction associated with administration of pembrolizumab.

NCI CTCAE Grade	Treatment	Premedication at subsequent dosing
Grade 1 Mild reaction; infusion interruption not indicated; intervention not indicated	Increase monitoring of vital signs as medically indicated until the subject is deemed medically stable in the opinion of the investigator.	None

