Grade 3 and Grade 4	Withhold pembrolizumab Discontinue at investigator discretion for safety/tolerability or if unable to reduce corticosteroid dose to < 10 mg per day prednisone equivalent within 12 weeks of toxicity	Systemic corticosteroids are indicated in addition to appropriate symptomatic treatment. May utilize 1 to 2 mg/kg prednisone or equivalent per day. Steroid taper should be considered once symptoms improve to Grade 1 or less and tapered over at least 4 weeks.

Table 7: General Approach to Handling irAEs not otherwise specified

All AEs are to be graded according to National Cancer Institute Common Terminology Criteria for Adverse Events (NCI CTCAE), version 4.0 (http://ctep.cancer.gov).

If an irAE does not resolve or improve to \leq Grade 1 within 12 weeks after last administration of pembrolizumab, study therapy discontinuation should be considered after discussion with the PI.

 Table 8: Dose Modifications and Management of Nausea/Vomiting Thought Related

 to Pembrolizumab*

Nausea/Vomiting	Management	Next Dose					
≤ Grade 1	Supportive care	No change in dose					
Grade 2	Hold until \leq Grade 1.	Hold until \leq Grade 1. Resume at same dose level.**					
Grade 3	Hold until < Grade 2.	Hold until < Grade 2. Resume at same dose level.**					
Grade 4	Off protocol therapy	Off protocol therapy if attributed to study drugs					
*If nausea/vomiting thought unrelated, dosing of study drugs is per investigator discretion							
**Participants requiring a delay of >12 weeks should go off pembrolizumab if nausea/							
vomiting thought related to pembrolizumab.							
Recommended manag	ement for all grades: antiemetics.						

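### Table 7 leaves stopping pembrolizumab to investigator discretion after a grade 4 immune-related event not otherwise specified, where Table 5 requires a permanent stop and no sentence ranks the two tables

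*Combined protocol and SAP*

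**What the plan says.** Three texts in Section 6.1 cover a grade 4 immune-related event that has no row or section of its own.

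- **Table 5, All Other Drug-Related Toxicity row.** At grade 4 both the restart column and the discontinuation column read "Permanently discontinue". At grade 3 (and intolerable or recurrent grade 2) treatment restarts on resolution to grade 0–1, and the discontinuation rule is "Toxicity does not resolve within 12 weeks of last dose or inability to reduce corticosteroid to 10 mg or less of prednisone"; that dose is a daily one, other steroids count at their equivalent, and the taper also has a limit of 12 weeks.
- **Other/Miscellaneous Immune Related Toxicities.** Its scope includes "Any additional Grade 3 or higher event, which the physician considers to be immune related". Grade 3 is a hold; grade 4 reads "Discontinue pembrolizumab".
- **Table 7, the general approach to irAEs not otherwise specified.** Grades 3 and 4 share one row: withhold, then "Discontinue at investigator discretion for safety/tolerability or if unable to reduce corticosteroid dose to < 10 mg per day" of prednisone equivalent within 12 weeks of toxicity.

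Two pieces of text bear on precedence. Table 5's caption calls the table a summary and adds "see more detailed recommendations for each event below the table". Table 7's caption limits it to events not otherwise specified. Neither says which table prevails.

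**The concern.** Grade 4 means life-threatening. For such an event Table 5 and the miscellaneous text leave the investigator no choice, while Table 7 makes stopping discretionary unless the steroid taper fails. An investigator who turns to Table 7, whose caption appears to fit an unlisted irAE exactly, finds a softer instruction than the one earlier in the same section. What is at stake is whether both sites handle a life-threatening immune event alike, in a trial whose Section 13.5 notes that no safety data exist for the combination.

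**Working it through.** There is no plan figure to reproduce. The check is a comparison of texts, followed by a rough calculation of how many patients could be concerned.

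**1. Do the texts overlap?** Section 7.1.1.1 defines an irAE as an event associated with exposure to study drug. An irAE is therefore within Table 5's residual row for drug-related toxicity as well as within Table 7. The same section lists myositis, arthritis and vasculitis among immune-mediated reactions, and none of them has a Table 5 row or a named place in Section 6.1. The overlap is real. Events with their own rule, and grade 4 events that are not immune-related, fall outside the point.

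**2. Do they agree at grade 4?**

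- Table 5 residual row: permanent stop.
- Miscellaneous immune text: stop.
- Table 7: withhold; stop at discretion or on a failed taper.

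Table 7 is the outlier.

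**3. Is there a precedence rule?** Sections 5 and 6 contain none. The sentence introducing Table 5 makes withholding according to that table mandatory but does not mention Table 7. By inference Table 7 yields, because its caption confines it to events not otherwise specified and a grade 4 irAE is already specified by the other two catch-alls. On that inference the grade 4 half of the Table 7 row has no case left to govern. Either reading leaves a cell that needs correcting.

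**4. How many patients?** Arm A has 30 planned patients (Section 13.5; two thirds of 45). The documents give no rate for grade 4 irAEs without their own rule, so the rate p is an assumption, taken from 0.1% to 1%. Expected patients = 30 × p; chance of at least one = 1 − (1 − p)^30.

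- p = 0.001: 30 × 0.001 = 0.03 expected; 1 − 0.999^30 = 3.0%
- p = 0.005: 30 × 0.005 = 0.15 expected; 1 − 0.995^30 = 14.0%
- p = 0.01: 30 × 0.01 = 0.30 expected; 1 − 0.99^30 = 26.0%

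An even chance of one such patient needs p = 1 − 0.5^(1/30) = 2.3%. These figures count patients to whom the conflicting texts would apply, not patients re-dosed. Re-dosing would also require resolution, a successful taper and a decision to restart.

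**The case against.** The strongest reply is that the protocol already answers the question. Two of the three texts order a stop, Table 7's caption makes it residual, and an investigator who stops pembrolizumab complies with all three. Much of this stands, and it keeps the point minor. It does not remove the defect, because the answer has to be inferred and the permissive cell stays in print.

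Four stronger readings are tempting, and the documents do not support them.

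- **That Table 5's caption hands authority to Table 7.** The caption points to detail for each event below the table. For these events that detail is first the miscellaneous section, which agrees with Table 5.
- **That Table 7 authorises rechallenge.** It has no restart instruction. Restart timing is in Table 5, which rules it out at grade 4, and the miscellaneous text mentions restarting only under grade 3. A reader would have to infer permission from Table 7's silence.
- **That the miscellaneous text is itself weaker because it omits the word permanently.** Section 6.1 uses the plain verb where Table 5 says permanently for grade 3–4 pneumonitis, grade 4 hyperthyroidism, grade 3 hepatic events and grade 3–4 renal events, and it calls temporary stops holds. The difference is editorial.
- **That the sentence under Table 7 on irAEs unresolved at 12 weeks is a second contradiction.** It says "study therapy discontinuation should be considered after discussion with the PI". Study therapy can mean the whole regimen, including radium-223. For pembrolizumab, Section 5.1 already provides that after more than 12 weeks' hold for drug-related toxicity "the patient should be discontinued from the offending agent", and Section 6 sets the same maximum hold.

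**Conclusion.** The inconsistency stands in limited form. For grade 4 irAEs without their own row or section, Table 7 is more permissive than the two other texts that cover them, and nothing states expressly that it yields. That rests on the wording alone, not on the assumed rates.

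The size is minor. Only Arm A is concerned, and probably very few patients. Existing safeguards reduce the risk further: Table 7 itself requires withholding, grade 3 or higher events considered immune-related go to the Sponsor-Investigator within 24 hours (Section 6.1), and life-threatening complications require immediate notice to the Overall PI (Section 5.4). These safeguards do not say whether dosing may resume.

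A reader might infer some effect on the trial's conclusions. There is none: endpoints, sample size, the early safety rule in Section 13.5 and the analyses do not depend on this row.

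**What to change.** Split the combined row of Table 7.

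- *Grade 4:* pembrolizumab is permanently discontinued.
- *Grade 3, following Table 5:* withhold until grade 0–1; discontinue if the event has not resolved by 12 weeks after the last dose, or if the steroid cannot be brought down to 10 mg or less of prednisone (or equivalent) daily within 12 weeks; the investigator may discontinue earlier.

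Add one sentence: *Where Table 7 and Table 5 differ, Table 5 governs.*

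The miscellaneous immune text and the 12-week sentence under Table 7 can stay as they are. Rewriting the latter for pembrolizumab alone would narrow its scope and remove the discussion with the PI.

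The cost is one row split and one added sentence in a protocol amendment. The grade 3 wording adds no rule that Table 5 does not already contain; it also moves Table 7's steroid threshold from below 10 mg to 10 mg or less, as in Table 5. Data collection, sample size and analysis do not change.

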6.2 Dose Modifications for Radium-223

Every effort should be made to administer the full dosing regimen of radium-223. **Adjustment of dose level is not permitted.** Study visits during the treatment period should occur at 4 week intervals (within a window of +/- 7 days). Dosing delays may be instituted under the following circumstances:

Myelosuppression:

Treatment-related changes in hematology parameters may occur.

- If a patient experiences CTCAE version 4.0 grade 3 or 4 neutropenia, thrombocytopenia, or anemia the administration of study drug should be delayed until recovery to grade 2 or better.
- If a patient experiences CTCAE version 4.0 grade 3 or 4 neutropenia, thrombocytopenia, or anemia **lasting 8 weeks**, further Radium-223 administrations must be discontinued.
- Blood transfusion is acceptable between Radium-223 administrations.

Spinal Cord Compression:

If the patient experiences spinal cord compression during the treatment period, the patient should be treated for the event, and may receive further study drug administration if adequately recovered.

Surgical Intervention:

If surgery is required, the patient should continue with study treatment, if this is considered safe in the treating investigator's opinion. The surgeon needs to be notified that the patient has been given radioactive drug, and needs to follow the guidelines for radioactive protection.

Non-pathological fractures:

For traumatic fractures in weight-bearing bones during treatment phase, Radium-223 administration should be delayed for at least 2-4 weeks from the time of fracture.

Pathological fractures:

Pathological fractures may occur as the result of either progressive disease or increased physical activity associated with significant pain palliation. Pathologic fractures are to be treated in a manner that attempts to maintain the best functional status and quality of life. Study treatment may continue as planned.

Other Radium-223 related toxicities:

- If a patient experiences CTCAE version 4.0 grade 3 or 4 toxicity related to radium-223, the administration of radium-223 should be delayed until recovery to grade 2 or better.
- If a patient experiences CTCAE version 4.0 grade 3 or 4 toxicity related to radium-223 lasting 8 weeks, further study drug administrations must be discontinued.

7. ADVERSE EVENTS: LIST AND REPORTING REQUIREMENTS

Adverse event (AE) monitoring and reporting is a routine part of every clinical trial. The following list of reported and/or potential AEs (Section 7.1) and the characteristics of an observed AE (Section 7.2) will determine whether the event requires expedited reporting **in addition** to routine reporting.

An adverse event is defined as any untoward medical occurrence in a patient or clinical investigation subject administered a pharmaceutical product and which does not necessarily have to have a causal relationship with this treatment. An adverse event can therefore be any unfavorable and unintended sign (including an abnormal laboratory finding, for example), symptom, or disease temporally associated with the use of a medicinal product or protocol-specified procedure, whether or not considered related to the medicinal product or protocol-specified procedure. Any worsening (i.e., any clinically significant adverse change in frequency and/or intensity) of a preexisting condition that is temporally associated with the use of the Merck's product, is also an adverse event.

Adverse events may occur during the course of the use of Merck product in clinical trials or within the follow-up period specified by the protocol, or prescribed in clinical practice, from overdose (whether accidental or intentional), from abuse and from withdrawal.

Adverse events may also occur in screened subjects during any pre-allocation baseline period as a result of a protocol-specified intervention, including washout or discontinuation of usual therapy, diet, placebo treatment or a procedure.

Progression of the cancer under study is not considered an adverse event unless it is considered to be drug related by the investigator.

All adverse events will be recorded from the time the consent form is signed through 30 days following cessation of treatment and at each examination on the Adverse Event case report forms/worksheets.

